In other words, you could not go on living with this pain or how you were feeling? Or was it to get attention, revenge or a reaction from others? Or both?

it was completely to get attention\\, revenge or a reaction from others

it was mostly to get attention\\, revenge or a reaction from others

equally to get attention\\, revenge or a reaction from others and to end or stop the pain

mostly to end or stop the pain \\(that is\\, you could not go on living with the pain or how you were feeling\\)

completely to end or stop the pain

Q03aNRT

You indicated before that since your last interview you had thought about how you might kill yourself. We want to ask you a few more questions about that.

When responding to these questions, we want you to think about the time you were feeling the most suicidal in the past [num] days.

If days SLC > 120

You indicated before that since your last interview you had thought about how you might kill yourself. We want to ask you a few more questions about that.

When responding to these questions, we want you to think about the time you were feeling the most suicidal since your last interview.

Q03a

When you were feeling most suicidal, how often did you think about how you might kill yourself?

less than once a week

about once a week

2 to 5 times a week

daily or almost daily

many times a day

Q03b

When you had these thoughts, how long did they last?

fleeting\\, lasting seconds to minutes

less than an hour

between 1 and 4 hours

between 4 and 8 hours

more than 8 hours

Q03c
Did you make any attempt to try to control or stop these thoughts, whether you were successful in controlling them or not?
Yes
No
Q03d
How easily could you control or stop thinking about how you might kill yourself?
easily controlled these thoughts
with a little difficulty
with some difficulty
with a lot of difficulty
unable to control these thoughts
Q03e.1
Did you think about things like family, religion, or fear of pain or death that might affect your decision about killing yourself?
Yes
No
Q03e
Choose one of the following statements that best describes whether anyone or anything did or did not stop you from acting on your thoughts of committing suicide.
something definitely stopped you
something probably stopped you
you are uncertain whether something stopped you
something most likely did not stop you
something definitely did not stop you

Q03f.1

When you thought about killing yourself, did you have a reason in mind like ending your pain or getting attention or revenge?

Yes

No

Q03f

What sort of reasons did you have for thinking about wanting to kill yourself? Was it to end the pain or stop the way you were feeling?

In other words, you could not go on living with this pain or how you were feeling? Or was it to get attention, revenge or a reaction from others? Or both?

it was completely to get attention\\, revenge or a reaction from others

it was mostly to get attention\\, revenge or a reaction from others

equally to get attention\\, revenge or a reaction from others and to end or stop the pain

mostly to end or stop the pain \\(that is\\, you could not go on living with the pain or how you were feeling\\)

completely to end or stop the pain

Q04aNRT

You indicated before that since your last interview you thought about killing yourself and that you had some intention of acting on these thoughts. We want to ask you a few more questions about that.

When responding to these questions, we want you to think about the time you were feeling the most suicidal in the past [num] days.

If days SLC > 120

You indicated before that since your last interview you thought about killing yourself and that you had some intention of acting on these thoughts. We want to ask you a few more questions about that.

When responding to these questions, we want you to think about the time you were feeling the most suicidal since your last interview.

Q04a

When you were feeling most suicidal and had some intention of acting on those thoughts of killing yourself, how often did those thoughts occur?

- less than once a week
- about once a week
- 2 to 5 times a week
- daily or almost daily
- many times a day

Q04b

How long did the thoughts last?

- fleeting\\, lasting seconds to minutes
- less than an hour
- between 1 and 4 hours
- between 4 and 8 hours
- more than 8 hours

Q04c

Did you make any attempt to **try** to control or stop these thoughts about actually killing yourself, whether you were successful in controlling them or not?

Yes

No

Q04d

How easily could you control or stop thinking about killing yourself?

- easily controlled these thoughts
- with a little difficulty
- with some difficulty
- with a lot of difficulty

unable to control these thoughts

Q04e.1

Did you think about things like family, religion, or fear of pain or death that might affect your decision about killing yourself?

Yes

No

Q04e

Choose one of the following statements that best describes whether anyone or anything did or did not stop you from acting on your thoughts of committing suicide.

something definitely stopped you

something probably stopped you

you are uncertain whether something stopped you

something most likely did not stop you

something definitely did not stop you

Q04f.1

When you thought about killing yourself, did you have a reason in mind like ending your pain or getting attention or revenge?

Yes

No

Q04f

What sort of reasons did you have for thinking about wanting to kill yourself? Was it to end the pain or stop the way you were feeling?

In other words, you could not go on living with this pain or how you were feeling? Or was it to get attention, revenge or a reaction from others? Or both?

it was completely to get attention\\, revenge or a reaction from others

it was mostly to get attention\\, revenge or a reaction from others

equally to get attention\\, revenge or a reaction from others and to end or stop the pain

mostly to end or stop the pain \\\(that is\\, you could not go on living with the pain or how you were feeling\\)

completely to end or stop the pain

Q05aNRT

You indicated before that since your last interview you had started working on plans or had actually worked out the details of how to kill yourself and had some intention to act on them. We want to ask you a few more questions about that.

When responding to these questions, we want you to think about the time you were feeling the most suicidal in the past [num] days.

If days SLC > 120

You indicated before that since your last interview you had started working on plans or had actually worked out the details of how to kill yourself and had some intention to act on them. We want to ask you a few more questions about that.

When responding to these questions, we want you to think about the time you were feeling the most suicidal since your last interview.

Q05a

When you were feeling the most suicidal and started planning or worked out details of how to kill yourself, how often did you think about killing yourself?

less than once a week

about once a week

2 to 5 times a week

daily or almost daily

many times a day

Q05b

How long did the thoughts last?

fleeting\\, lasting seconds to minutes

less than an hour

between 1 and 4 hours

between 4 and 8 hours

more than 8 hours

Q05c

Did you make any attempt to **try** to control or stop these thoughts about actually killing yourself, whether you were successful in controlling them or not?

Yes

No

Q05d

How easily could you control or stop thinking about killing yourself?

easily controlled these thoughts

with a little difficulty

with some difficulty

with a lot of difficulty

unable to control these thoughts

Q05e.1

Did you think about things like family, religion, or fear of pain or death that might affect your decision about killing yourself?

Yes

No

Q05e

Choose one of the following statements that best describes whether anyone or anything did or did not stop you from acting on your thoughts of committing suicide.

something definitely stopped you

something probably stopped you

you are uncertain whether something stopped you
something most likely did not stop you
something definitely did not stop you

Q05f.1

When you thought about killing yourself, did you have a reason in mind like ending your pain or getting attention or revenge?

Yes

No

Q05f

What sort of reasons did you have for thinking about wanting to kill yourself? Was it to end the pain or stop the way you were feeling?

In other words, you could not go on living with this pain or how you were feeling? Or was it to get attention, revenge or a reaction from others? Or both?

it was completely to get attention\\, revenge or a reaction from others

it was mostly to get attention\\, revenge or a reaction from others

equally to get attention\\, revenge or a reaction from others and to end or stop the pain

mostly to end or stop the pain \\(that is\\, you could not go on living with the pain or how you were feeling\\)

completely to end or stop the pain

Midpoint Transition (NRT02)

We are almost finished.

So far we have been asking about thoughts and feelings you may have had.

Now we would like to know about things you may have done to try to hurt yourself since your last interview.

Suicidal Behavior

Q06a

Since your last interview on [day] [date] have you made a suicide attempt?

Yes
No
Q06b
Use the number keys to enter the number of suicide attempts you have made since your last interview.
Q06cNRT01
If attempts >= 3
Consider your most recent attempt, your first attempt, and your most serious attempt separately.
Q06cNRT02
If attempts = 2
Consider your most recent attempt and your first attempt separately
Q06c
If loop = 1
When you made your most recent attempt, were you trying to end your life?
Yes
No
If loop = 2
When you made your first attempt, were you trying to end your life?
Yes
No
If loop = 3
When you made your most serious attempt, were you trying to end your life?
Yes
No

Q06e
Did you think it was possible that you could have died from what you did?
Yes
No
Q06d
So then
you wanted to die\\, even a little\\, when you did this
you did it purely for other reasons\\, like to relieve stress\\, feel better\\, get sympathy\\, or get something else to happen to you\\, without any intention of killing yourself
Q07a
Since your last interview, have you done anything to intentionally hurt or harm yourself?
Yes
No
Q07b
Use the number keys to enter the number of times you have intentionally hurt or harmed yourself since your last interview. If you cannot remember the exact number, enter your best estimate.
Q07cNRT01
Just consider the three most recent times you have intentionally harmed or hurt yourself.
Q07c_Attempt
If loop = 1
Think about the time you intentionally hurt or harmed yourself most recently.

If loop > 1
Consider the time you hurt or harmed yourself before that
Q07c
Were you trying to end your life?
Yes
No
Q07e
Did you think it was possible that you could have died from what you did?
Yes
No
Q07d
So then
you wanted to die\\, even a little\\, when you did this
you did it purely for other reasons\\, like to relieve stress\\, feel better\\, get sympathy\\, or get something else to happen to you\\, without any intention of killing yourself
Q08a
Since your last interview, have you done anything dangerous where you could have died?
Yes
No
Q08b
Use the number keys to enter the number of times you have done dangerous activities where you could have died in the past [num] days.

If days SLC > 120
Use the number keys to enter the number of times you have done dangerous activities where you could have died since your last interview.
Q08c_NRT01
Just consider the three most recent times you have done something dangerous where you could have died.
Q08c_Attempt
If loop = 1
Think about the most recent time you did a dangerous activity where you could have died
If loop > 1
Consider the time you did something dangerous before that
Q08c_1
Were you trying to harm yourself when you did this?
Yes
No
Q08c
Were you trying to end your life?
Yes
No
Q08d
So then
you wanted to die\\, even a little\\, when you did this

you did it purely for other reasons\\, like to relieve stress\\, feel better\\, get sympathy\\, or get something else to happen to you\\, without any intention of killing yourself

Lethality

Q09

If Q06a = YES

As a result of your **most serious** attempt since your last interview, were you injured more seriously than surface scratches or mild nausea?

Yes

No

If Q06a = NO

As a result of the **most serious** time you tried to hurt yourself since your last interview, were you injured more seriously than surface scratches or mild nausea?

Yes

No

Q09a

Were you hospitalized for **medical** treatment of the physical injury you suffered?
For example, were you comatose from an overdose, or did you suffer extensive blood loss that required a transfusion, or severe damage to your head or a vital organ?
If you were hospitalized for psychiatric evaluation, but not for medical treatment of a severe physical injury, answer No.

Yes

No

Q09b

Were you injured so severely that you would have died without treatment in an intensive care unit, or did you suffer permanent physical damage from which you will never completely recover, such as paralysis or disfigurement?

Yes
No
Q09c
Did your injury cause you to be extremely drowsy, or result in broken bones, or severe bleeding?
Yes
No
Q09.10
Although you were not injured during the most serious time, how serious could your injuries have been?
what you did was not likely to cause injury
what you did was likely to cause physical injury\\, but probably not death
what you did was likely to cause death with or without medical help\\, for example trying to shoot yourself in the head but the gun failed to fire
Interrupted Attempts
Q10
Since your last interview, was there a time when you started to do something to end your life, but someone or something stopped you before you actually did anything?
Yes
No
Q10a
About how many times have you been stopped from ending your life by someone or something since your last interview?
Please enter the number.

Aborted Attempts
Q11
Since your last interview, has there been a time when you started to do something to try to end your life, but you stopped yourself before you actually did anything?
Yes
No
Q11a
About how many times have you stopped yourself from ending your life in the last [num] days, since your last interview?
If days SLC > 120
About how many times have you stopped yourself from ending your life since your last interview?
Please enter the number.
Preparatory Acts or Behaviors
Q12NRT
Asses prior responses and present introduction:
Other than the times you have already told us about since your last interview when you did things intending to kill yourself or thought you might have died, when you started to do something to end your life but someone or something stopped you, and when you started to do something to end your life but stopped yourself,
Other than the times you have already told us about since your last interview when you did things intending to kill yourself or thought you might have died, and when you started to do something to end your life but stopped yourself,
Other than the times you have already told us about since your last interview when you did things intending to kill yourself or thought you might have died and when you started to do something to end your life but someone or something stopped you

Other than the times you have already told us about since your last interview when you started to do something to end your life but someone or something stopped you and when you started to do something to end your life but stopped yourself,

Other than the times you have already told us about since your last interview when you did things intending to kill yourself or thought you might have died,

Other than the times you have already told us about since your last interview when you started to do something to end your life but someone or something stopped you,

Other than the times you have already told us about since your last interview when you started to do something to end your life but stopped yourself,

Q12

Have you taken any steps toward making a suicide attempt or preparing to kill yourself, such as collecting pills, getting a gun, giving valuables away or writing a suicide note?

Yes

No

Q12a

About how many times?

Please enter the number.

Exit

You have completed your interview. Thank you and Good bye.

Appendix 15 Guidance for re-screening

It is permitted to re-screen subjects once if the reason for non-eligibility was transient (e.g., abnormal laboratory test, insufficient wash-out period of a forbidden medication), provided that documented authorization has been received from Actelion. Re-screening requires re-consenting i.e., a new Informed Consent Form must be signed by the subject and the PI.

- If the screening failure was due to a laboratory result (i.e., one or more hematology variables and/or one or more biochemistry variables were out of eligibility range) from Visit 1 (Screening):
 - All hematology and/or blood chemistry assessments from Visit 1 (Screening) need to be repeated and will then be used for assessing eligibility.
 - Other pre-randomization assessments do not need to be repeated if performed within 90 days (with the exception of 12-lead ECG and pregnancy test which should be performed within 37 days) prior to the date of re-screening and if their outcome was not exclusionary.
- If the screening failure was due to a laboratory result from Visit 2 (Baseline):
 - Laboratory assessments from Visit 2 (Baseline) must be repeated.
 - Laboratory assessments from Visit 1 (Screening) must be repeated unless performed within 37 days prior to the re-screening. In this case, laboratory assessments at Visits 1 and 2 (re-screening) must be performed at least 21 days apart.
 - Other pre-randomization assessments do not need to be repeated if performed within 90 days (with the exception of 12-lead ECG and pregnancy test which should be performed within 37 days) prior to the date of re-screening and if their outcome was not exclusionary.
- If the reason for screening failure was due to an assessment other than laboratory tests:
 - The assessment leading to the screening failure has to be repeated.
 - Other pre-randomization assessments do not need to be repeated if performed within 90 days prior to the date of re-screening (with the exception of 12-lead ECG, hematology, blood chemistry and pregnancy test which should be performed within 37 days) and if the outcome was not exclusionary.

- If the screening failure was due to more than one assessment (e.g., laboratory and dermatological assessments) and the re-screening was authorized by Actelion:
 - All pre-randomization assessments have to be repeated.

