subjects who appear eligible based on the assessments made during this visit will be provided with the FSIQ-RMS. Once the results from the laboratory tests confirm the subject's eligibility, and provided no other assessment performed in the meantime excludes the subject, the site coordinator will contact the subject to instruct him/her to start the completion of the FSIQ-RMS. At home, the subject will complete the symptom domain of the FSIQ-RMS for 7 days (i.e., section 1 of the questionnaire). On the 7th day, the subject will also complete the impacts domain of the FSIQ-RMS (i.e., section 2 of the questionnaire).

- (5) Healthcare resource utilization data, including number of hospital visits, length of stay, number of Intensive care unit admissions for MS relapses and emergency medical services facility visits for MS.
- (6) Any CXR that has been performed within 90 days prior to Visit 1 (Screening) can be used (in this case, no need to repeat CXR at Visit 1 [Screening]).
- (7) Dermatological examination to be performed by a dermatologist [see Section 7.3.12]. In case of re-screening, skin examination does not need to be repeated if skin examination from initial screening was performed within 90 days prior to the date of re-screening.
- (8) Height only at Visit 1 (Screening).
- (9) SBP/DBP: Pre-dose and hourly (\pm 15 minutes) for at least 4 hours post-dose and up to 12 hours.
- (10) Only pre-dose ECGs at all visits except Visit 3 (Day 1), and Visit 6 (Week 12).
- (11) Pre-dose and hourly (\pm 15 minutes) for at least 4 hours post-dose ECGs and up to 12 hours on Day 1. Pre-dose and 3 hour (\pm 15 minutes) post-dose at Week 12.
- (12) OCT and/or ophthalmological examination to be performed at any visit in the presence of visual symptoms suggestive of macular edema or active uveitis.
- (13) Total lymphocyte counts will be tested every 4 weeks (\pm 3 days) up to Week 24 (i.e., additional lymphocyte tests will be performed at Week 8, Week 16, and Week 20) and every 12 weeks thereafter.
- (14) Lymphocyte subset analysis will be performed on a subset of at least 200 subjects randomized to the main study.
- (15) Serum pregnancy test at Visit 1 (Screening), urine pregnancy test at all subsequent visits. Urine pregnancy tests (performed at home) on a 4-weekly basis (\pm 4 days) between the visits during the study (results of the pregnancy test to be communicated by telephone call to the principal investigator / treating neurologist).

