4.3 Inclusion criteria

For inclusion in the study, all of the following inclusion criteria must be fulfilled. It is not permitted to waive any of the criteria for any subject:

1. Signed informed consent prior to initiation of any study-mandated procedure.
2. Males and females aged 18 to 55 years (inclusive).
3. A woman of childbearing potential (WOCBP) is eligible only if the following applies:
 - must have a negative serum pregnancy test at Visit 1 (Screening) and a negative urine pregnancy test at Visit 2 (Baseline);
 - must agree to undertake monthly urine pregnancy tests during the study and up to 30 days after study treatment discontinuation;
 - must use reliable methods of contraception until 30 days after study treatment discontinuation as described in Section 4.5.2;

Definition of WOCBP and the acceptable methods of contraception for this study are described in Section 4.5.

4. Presenting with a diagnosis of MS as defined by the revised (2010) McDonald Diagnostic Criteria for MS [see [Appendix 2](#)] with relapsing course from onset (i.e., RRMS, or SPMS with superimposed relapses).
5. Ongoing treatment with DMF for at least 6 months prior to Visit 1 (Screening).
6. Active disease after at least 3 months of DMF treatment defined by at least one of the following features:
 - At least one MS attack supported by objective neurological examination with onset within 12 months to 1 month prior to baseline EDSS assessment;
 - At least one Gd+ lesion on an MRI of the brain or spinal cord, performed either within 12 months prior to Visit 1 (Screening) or during the pre-randomization period (MRI assessed at Visit 2 [Baseline] may be the qualifying scan);
 - Presence of at least one new or one unequivocally enlarging T2 lesion on an MRI of the brain or spinal cord, assessed by comparing two MRI scans: the first MRI scan must be performed within 15 months prior to Visit 1 (Screening) and after at least 3 months of DMF treatment; the second MRI scan must be performed prior to randomization (MRI assessed at Visit 2 [Baseline] may be used). The presence of at least one new or one unequivocally enlarging T2 lesion has to be confirmed by the MRI central reading facility prior to randomization.
7. Ambulatory and with an EDSS score between 0 and 6.0 (inclusive) at Visit 1 (Screening) and Visit 2 (Baseline).
8. For subjects with ongoing treatment with DMF \geq 12 months prior to screening:

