- Subjects receiving non-live vaccination while on study treatment will have 5 mL of blood drawn prior to and \geq 3 weeks after vaccination in order to explore changes in vaccine-specific antibody titers from pre- to post-vaccination. Samples are to be stored at the central laboratory to be analyzed at the end of the study.

Test for TB

- An IFN gamma release assay will be performed at Visit 1 (Screening) to screen for active or latent TB [see Section [7.3.5](#)].

Pregnancy test

A serum pregnancy test for WOCBP will be performed at Visit 1 (Screening), Visit 20 (FU), and if pregnancy is suspected during the study. Urine pregnancy tests will be performed at Visit 2 (Baseline), Visit 4 (Week 2), Visit 5 (Week 4), Visit 6 (Week 12), and every 12 weeks thereafter up to Visit 17 (Week 144), and at Visit 18 (EOT). Additionally, urine pregnancy tests will be performed at home every 4 weeks (\pm 4 days) between the visits. Subjects will communicate the result (telephone call) of the tests to the principal investigator / treating neurologist.

In order for WOCBP to be randomized in the study, they must have a confirmed negative serum pregnancy test at Visit 1 (Screening) and a second confirmed negative urine pregnancy test at Visit 2 (Baseline) prior to randomization. **The two tests must be performed a minimum of 21 days apart.**

Serum pregnancy testing results will be automatically transferred from the central laboratory database to Actelion's clinical database. Urine pregnancy testing results will be recorded in the eCRF. In case of pregnancy, a Pregnancy Form must be completed [see Section [10.3](#)].

Urinalysis

- pH
- Glucose
- Proteins
- Blood
- Leukocytes
- Bilirubin, urobilinogen

Urinalysis will be assessed using dipsticks at Visit 1 (Screening), Visit 6 (Week 12), Visit 7 (Week 24), and every 24 weeks thereafter up to Visit 17 (Week 144), Visit 18 (EOT), and Visit 20 (FU). If applicable, urinalysis will also be performed at all

corresponding visits in the PTOP. In addition, unscheduled urinalysis may be performed at any time during the study (Visits U1, U2, etc.).

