It is permitted to re-screen subjects once if the reason for non-eligibility was transient (e.g., abnormal laboratory test, insufficient wash-out period of a forbidden medication), provided that documented authorization has been received from Actelion. Re-screening requires re-consenting i.e., a new ICF must be signed by the subject and by the investigator. All pre-randomization assessments do not need to be repeated at the time of re-screening if they were performed within 90 days or within 37 days for laboratory (i.e., hematology, blood chemistry, and pregnancy test). The guidance indicating which test needs to be repeated at the time of the re-screening authorization is provided in [Appendix 15](#).

The randomization must occur within 45 days from the date of Visit 1 (Screening; i.e., date of signature of the informed consent) or, in case of re-screening, within 45 days from the date of re-screening (i.e., date of signature of the new informed consent).

Unscheduled visits may be performed at any time during the study. Depending on the reason for the unscheduled visit (e.g., AE), appropriate assessments will be performed based on the judgment of the investigator and the results will be recorded in the CRF. After an unscheduled visit, the regular scheduled study visits must continue according to the planned visit and assessment schedule.

[figure not shown]

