8.2.1 Visit 3 – Randomization Day 1 – Randomization and post-dose assessments

The treatment period starts with first dose taken during Visit 3 (Day 1 of the study).

The randomization must occur within 45 days from the date of Visit 1 (Screening; i.e., date of signature of the informed consent) or, in case of re-screening, within 45 days from the date of re-screening (i.e., date of the first assessment performed as part of the re-screening).

If eligible, the subject should be randomized in the study, and take the first dose of study drug. The subject must be monitored for up to 12 hours post-dose. Starting at 4 hours post-dose, the first-dose administrator must check whether the subject fulfills the discharge criteria from cardiac monitoring [see Section 5.1.10]. Subjects may be discharged from cardiac monitoring if they meet the discharge criteria before 12 hours post-dose but no sooner than the (report of) 4 hours post-dose ECG has been evaluated by the first-dose administrator [see Section 5.1.10].

Visit 3 post-dose assessment includes:

- After confirmation of eligibility (i.e., verification of all entry criteria) by the investigator:
 - Randomization via IRT to obtain randomization and study treatment kit number.
 - Dispensing of study treatment.
- SBP/DBP hourly (\pm 15 minutes) for up to 12 hours post-dose with a minimum of 4 hours post-dose (under the responsibility of the first-dose administrator).
- 12-lead ECG hourly (\pm 15 minutes) for up to 12 hours post-dose with a minimum of 4 hours post-dose (under the responsibility of the first-dose administrator).
- PK sampling at 3 hours (\pm 15 minutes) post-dose (**NB:** this should be performed after the corresponding hourly 12-lead ECG and SBP/DBP measurement).
- Recording of AEs and SAEs (**NB:** On Day 1, significant findings that, in view of the first-dose administrator, meet the definition of an AE, have an onset after the study drug intake, and are resolved at the time of discharge of the subject from cardiac monitoring, must be recorded directly on the AE page of the separate eCRF by the first-dose administrator / delegate. These AEs will not be visible to any of the blinded study personnel at the study site.).

- Remind WOCBP to use the methods of contraception defined for this study. The reminders must be documented in the hospital chart.

Schedule an appointment for next visit and instruct subject to:

- not take study treatment on the day of study visit prior to coming to the site.

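### Carried-over pregnancy tests are timed to the re-screening date, not to first dose, so the last listed negative test can be older than the 24 days implied by the ordinary route (61 days in the permitted worst case)

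*Protocol*

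**What the plan says.** **Carry-over.** For a screen failure on one non-laboratory assessment, Appendix 15 asks only for that assessment to be repeated. Others stay valid for 90 days before re-screening, "with the exception of 12-lead ECG, hematology, blood chemistry and pregnancy test which should be performed within 37 days". Section 8 states the same rule: "within 37 days for laboratory (i.e., hematology, blood chemistry, and pregnancy test". The two laboratory-failure branches of Appendix 15 also give the pregnancy test a 37-day window. Failure on more than one assessment means repeating everything.

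**Time to randomization.** Section 8 allows randomization "in case of re-screening, within 45 days from the date of re-screening (i.e., date of signature of the new informed consent". First dose is taken at that visit (Section 8.2.1).

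**Required tests.** A serum test at Visit 1 and a urine test at Visit 2 must both be negative, with the serum test first (Sections 7.3.13.2 and 8.1.2): "The two tests must be performed a minimum of 21 days apart".

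**Visit 3.** Section 7.3.13.2 goes from Visit 2 to Visit 4: "Urine pregnancy tests will be performed at Visit 2 (Baseline), Visit 4 (Week 2), Visit 5 (Week 4), Visit 6 (Week 12". The Visit 3 cell of the pregnancy-test row in Table 1 is empty, and Sections 8.1.3 and 8.2.1 list no test.

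**Text that could point the other way.** Inclusion criterion 3 says a woman "must agree to undertake monthly urine pregnancy tests during the study and up to 30 days after study treatment discontinuation". Table 1 footnote 15 says "Serum pregnancy test at Visit 1 (Screening), urine pregnancy test at all subsequent visits", and adds 4-weekly home tests between visits.

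**The concern.** The validity of a retained test is counted to re-screening, but what matters is how old the test is at first dose, and up to 45 further days may pass before that. The 12-lead ECG has the same 37-day carry-over but is repeated pre-dose on Day 1, so its age at re-screening is harmless. The pregnancy test has no such backstop in the visit lists.

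Sections 1.3.1 and 1.3.2.4 report embryotoxic and teratogenic potential, and exclusion criterion 1 bars pregnant women. If a woman conceives after a retained urine test and no further test is done, the next listed test is at Day 15, after the 14-day up-titration. Section 7.3.12 describes a realistic trigger: a skin lesion found at Visit 2, excised, and the woman re-screened.

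**Working it through.** The protocol states no maximum test age at first dose, so there is no stated figure to reproduce. Every figure below follows from its own windows.

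**Inputs**
- Pre-randomization period: at most 45 days (Section 8.1).
- Serum-to-urine gap: at least 21 days (Sections 7.3.13.2 and 8.1.2).
- Carry-over: at most 37 days before re-screening (Section 8, Appendix 15).
- Re-screening to randomization: at most 45 days (Section 8).
- Home tests: every 4 weeks ± 4 days (Table 1 footnote 15, Section 7.3.13.2).

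**Age of the last listed test at first dose**

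| Route | Formula | Maximum |
|---|---|---|
| Ordinary, no re-screening | 45 - 21 | 24 days |
| Both tests kept | (37 - 21) + 45 | 61 days |
| Serum kept, urine on re-screening day | 0 + 45 | 45 days |
| Both tests repeated after re-screening | 45 - 21 | 24 days |
| 4-weekly home tests applied from consent | 28 + 4 | about 32 days |

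Enumerating all whole-day schedules gives the same maxima for the first four rows.

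**Feasibility of the worst case.** Serum on day 0, urine on day 21, re-consent on day 37, randomization and first dose on day 82. The urine test is then 82 - 21 = 61 days old and the serum test 82 days old.

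**When 24 days is exceeded.** Let *a* be the age of a kept urine test at re-screening, between 0 and 37 - 21 = 16 days. The age at first dose passes 24 days when randomization is more than 24 - *a* days after re-screening. That is more than 8 days for *a* = 16 and more than 24 days for *a* = 0, out of 45 allowed.

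**Last listed test to the Day 15 test, without home tests.** 61 + 14 = 75 days, against 24 + 14 = 38 days by the ordinary route.

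**Branches.** The non-laboratory branch is the clearest. After a Visit 2 laboratory failure, Visit 2 laboratory assessments must be repeated. Section 8 counts the pregnancy test as laboratory, yet that branch also names it among the assessments that may be kept for 37 days.

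**The case against.** **Home testing may already cover the interval.** Criterion 3 and footnote 15 call for monthly or 4-weekly tests during the study, and Sections 5.2.1 and 10.1.5 date study start from informed consent. On that reading a test falls due before randomization and the age is capped at about 32 days. This is a fair reading. It cannot be dismissed because home kits are first listed for dispensing at Visit 6: a home test is due at Week 8, and the Visit 5 list shows no kits either. But the text is ambiguous. The Amendment 5 rationale describes the home tests as belonging to the treatment period, and 32 days still exceeds 24. Footnote 15's reference to all later visits would put a test at Visit 3, but the empty cell and three section lists contradict that.

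**24 days is not a protocol standard.** Correct. It is a by-product of 45 - 21, and the on-treatment interval of 4 weeks ± 4 days is longer. It serves only to show what the ordinary route delivers.

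**61 days is a corner case.** Correct. It needs the failure, its resolution, sponsor authorization and new consent all within 16 days of the urine test, and then the full 45 days. A reader might infer that re-screened women are typically dosed on two-month-old tests. The protocol supports only that this is permitted.

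**Other safeguards exist.** Contraception is mandatory (Section 4.5.2), eligibility is rechecked at Visit 3, and a serum test is done if pregnancy is suspected. These lower the risk, but none is a test at a fixed time before dosing. The ordinary route also lacks a Day 1 test, so waiting until Day 15 is not peculiar to re-screening. What differs is how old the preceding test may be.

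**Conclusion.** The point holds as a gap in the carry-over rule. The age of the last listed negative test at first dose can exceed the ordinary 24 days: up to 61 days with both tests kept, 45 days with only the serum test kept, and about 32 days if home testing is taken to start at consent. The worst case is 61 - 24 = 37 days beyond the ordinary route.

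The 61 days assume that no home or Visit 3 test is done and that the same re-screening date starts both clocks. The second assumption matters because Section 8 dates re-screening from the new consent, while Section 8.2.1 allows randomization "within 45 days from the date of re-screening (i.e., date of the first assessment performed as part of the re-screening".

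The affected group is small: one re-screening, a transient reason, a single failed assessment and sponsor authorization. The number of such women is not stated. A reader might take this as a breach of a stated 24-day limit, or as a 61-day gap that the protocol definitely fixes. Neither is supported: no limit is stated, and the home-test wording could close part of the interval. The change is worth making because a stated rule weakens a safeguard for a drug with teratogenic potential.

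**What to change.** In Section 8 and in every Appendix 15 branch that allows carry-over, including the laboratory-failure branches, require for each re-screened woman of childbearing potential a negative urine pregnancy test dated within 24 days before randomization, or taken pre-dose at Visit 3, whatever earlier tests are retained. Asking only for a urine test at some time before randomization would not be enough, because one done on the re-screening day could still be 45 days old at first dose.

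As a separate consistency edit, use one definition of the re-screening date in Sections 8 and 8.2.1.

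The cost is a wording change and at most one extra urine test, already a study procedure, per re-screened woman of childbearing potential.
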